#### ASSESSMENT OF POTENTIAL RISKS AND BENEFITS

The risk of the artificially intelligent therapist generating adverse responses/advice during the session is rationalized by the nature of the investigation being a feasibility study of the implementation of an Al-powered mental health support tool. We anticipate that the built-in safeguards which minimize the ability of the model to generate derogatory, unprofessional, or dangerous responses will greatly minimize the chances of this occurring. In internal pilot testing within our lab, which has included over 100 mock conversations to date, we have not yet experienced any perceived adversarial, derogatory, unprofessional, or harmful response or advice. Nonetheless, an important purpose of this feasibility study is to confirm safety and appropriateness of the system. Furthermore, the risk of emotional or psychological adverse events as a result of the interaction with the AI model will also be minimized by providing participants with access to a hot line (Appendix E) to licensed mental health workers who are available at all times free at charge to trainees at Cedars Sinai. At the beginning of each session, participants will be provided instruction on how to access the licensed mental health works should an adverse event occur. If participants feel they need immediate assistance or report concerning suicidal thoughts or ideation, XAIA can send an immediate text and email to our social worker who is not involved in trainee education and employment. Our social worker can then contact the trainee for immediate intervention and provide immediate psychiatric resources available to trainees. In addition, a psychiatrist who is not involved in the proposed participants training, will be available for any urgent psychiatric attention.

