### 5.2 Study Design and Duration

This is a prospective pilot study with internal medicine residents and gastroenterology fellows to evaluate the role of AI mental health support tool as a wellness resource.

Participants will be invited via e-mail to participate in the study. ]The invitation e-mail will describe the study and ask that those who meet exclusion criteria do not participate in this pilot study. The e-mail will also include a file with information of the study for participants to review including how study members are blinded and the de-coding process required for participants to be contacted by our social worker should they score  $\geq$ 15 on PHQ-9 and or  $\geq$ 10 on GAD-7. Those who choose to participate will be asked email our team member who is not involved in trainee education who will send the participants a REDCap link to the consent, survey and a code to be used in the survey.

Participants will be asked to complete a set of questionnaires (Appendix B, C and D) to evaluate their mental health and factors that contribute to mental health as well as four AI powered mental health support sessions over a four-week period. This will conclude the active phase of their participations. Participants will then be sent a questionnaire at 3 months from study initiation to complete a questionnaire evaluating their mental health and if they would be interested in additional AI powered mental health support sessions.

The questionnaires will be administered before the AI sessions and at the end of the study period to evaluate for changes in mental health scores. The questionnaires will include the validated PHQ-9 for a standardized depression score and the GAD-7 for a standardized anxiety score to evaluate symptoms related to depression and anxiety. In addition, a set of questions will focus on demographics, work and home environment to evaluate factors that may contribute to mental health prior to the AI sessions and a set of questions related to the AI sessions at the end of the study period. The questionnaire will be administered via REDCap.

To maintain subject safety and confidentiality the following work-flow will be followed.

- 1. Participants who choose to participate in the study will be given a redcap link for the consent form, survey and a code via e-mail. In order to complete the consent and survey, participants will have to enter the code provided to them.

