- 2. Our social worker will be the only study members with a list of the subject's email and code.
- 3. Our social worker will review the survey responses on redcap.
- 4. If a participant survey has as a score on the PHQ9 >15 and or GAD>10, our social worker will contact the participant for evaluation and provide additional resources as needed.

5. During the sessions, XAIA will be programed to send a text message to our social worker from participants who report actionable comments such as suicidal thoughts and concerns. Our social worker will be available to receive the messages from XAIA and contact the trainee for immediate intervention and connect the trainee to additional resources as needed. In addition, a psychiatrist physician will be available for any urgent psychiatric attention.

The AI powered sessions will be administered via a web browser such as a computer, laptop, tablets or cellphone. Participants can complete the session in the privacy of their home or in a private location at work such as a call-room. Participants will be asked to complete one 20-minute session per week during the 4-week study period for a total of four sessions.

The AI program used will be the XAIA software program. XAIA was developed at Cedars Sinai. Participants will be sent an email with the link to use the XAIA software. This includes a tutorial on how to use XAIA. Typical interactions with XAIA involve a process of XAIA initially probing for topics with general inquiries "So [name], how can I help?", then asking more indepth questions about a particular topic identified by the participant, and then offering support and/or coping methods about the identified problem or topic. Once XAIA is done speaking, the participant will answer the questions and press the "done speaking" button. XAIA then processes the messages and then replies. This process repeats until the participant informs XAIA that they wish to end the session and can click the "end session" button.

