#### **Questionnaires/surveys:**

This study involves the administration of questionnaires to evaluate scoring changes for depression and anxiety symptoms as a measurement for mental health wellness before and after the intervention. This information is routinely collected as part of clinical care with the PHQ-9 and GAD-7 questionnaires. The questionnaires will be administered at baseline and at the end of the 4-week study period. As part of the initial questionnaire, there will be a set of questions that aim to determine demographics as well as work-related and home-related factors that contribute to mental health will be administered prior to the AI powered sessions. At the completion of the 4-week session a questionnaire with a set of questions evaluating the use and acceptability of the AI mental health support will be administered. Finally, participants will be sent a questionnaire including the PHQ-9 and GAD-7 along with a set of questions evaluating their interest in participating in additional sessions at 3 months. The follow-up questionnaires will also provide information on active resources for mental health available to trainees at Cedas Sinai. In total, the questionnaires should take no longer than 20 minutes to complete at the beginning and end of the study period and no longer than 10 minutes at followup. The questionnaire will be administered electronically via REDCap. The study will not collect personal identifying information. The questionnaire will also contain a link with information on how to obtain immediate mental health assistance including a hot line as provided by GME to all trainees at Cedars Sinai. This includes access to a mental health professional who is on call for any psychiatric emergencies.

We will be conducting following questionnaires.

- Patient Health Questionnaire -9 (PHQ-9) Will be administered at the beginning and end of the study as part of Appendix B, C and D.
  - o This questionnaire is validated.
  - o The questionnaire is available in languages other than English.
- General Anxiety Disorder- 7 (GASD-7) will be administered at the beginning and end of the study as part of Appendix B, C and D.
  - o This questionnaire is validated.
  - o The questionnaire is available in languages other than English.
- Work and Home Environment will be administered only at the beginning of the study as part of Appendix B.
  - o This questionnaire is not validated.

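### Survey-driven contact depends on PHQ-9 or GAD totals alone, so a positive suicidal-thoughts answer below both cut-offs requires no contact by the study, most clearly at month 3

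*Protocol*

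**What the plan says.** Protocol section 5.2 sets out a numbered work-flow for participant safety and confidentiality. Three of its steps matter here.

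- **Step 3:** "Our social worker will review the survey responses on redcap". No action or time limit is attached.
- **Step 4:** "If a participant survey has as a score on the PHQ9 >15 and or GAD>10, our social worker will contact the participant". This is a rule on total scores.
- **Step 5:** during sessions, XAIA texts the social worker about messages "from participants who report actionable comments such as suicidal thoughts and concerns", and the social worker then contacts the trainee at once. No score is involved.

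Earlier in section 5.2, the information file for participants is said to explain "the de-coding process required for participants to be contacted by our social worker should they score" at least 15 on the PHQ-9 and/or at least 10 on the GAD-7. That description also uses totals only.

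The section on assessment of potential risks and benefits covers the same ground as step 5. If participants need immediate help or "report concerning suicidal thoughts or ideation, XAIA can send an immediate text and email to our social worker". That alert also runs through XAIA.

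On timing, section 5.2 says of the initial questionnaires and the four sessions over four weeks: "This will conclude the active phase of their participations". Section 5.3 adds the month-3 form: "Finally, participants will be sent a questionnaire including the PHQ-9 and GAD-7 along with a set of questions". The questionnaire also carries a "link with information on how to obtain immediate mental health assistance including a hot line", with access to an on-call mental health professional.

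**The concern.** The protocol handles the same disclosure in two ways. Suicidal thoughts reported to XAIA lead to contact with no threshold. The same thoughts reported on the PHQ-9 lead to required contact only if a total score is high enough. A total measures overall symptom burden and does not stand in for one answer about self-harm.

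This is a matter of participant safety. Section 2.0 gives suicide risk among physicians as part of the rationale and notes that only a minority of physicians use mental health services. Safeguards that rely on the participant to make the call are therefore weakest in this population. Under step 2, only the social worker holds the list linking codes to e-mail addresses, so no other study member is placed to identify and reach a respondent.

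**Working it through.** The protocol derives neither cut-off, so there is no figure to reproduce. The check has three parts.

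**1. Which rules require the study to make contact?**

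| Source of the disclosure | Stated trigger | Who must act |
|---|---|---|
| XAIA session (step 5; risk assessment) | Report of suicidal thoughts, no score | Social worker |
| Survey (step 4) | PHQ-9 above 15 and/or GAD above 10 | Social worker |
| Survey (participant information, 5.2) | PHQ-9 at least 15 and/or GAD-7 at least 10 | Social worker |
| Survey (step 3) | None; responses are reviewed | No action stated |
| Survey (5.3) | None; hotline and resource information | Participant |

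Section 7.1 adds only general reporting to the IRB. No rule attaches contact to a single survey answer.

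**2. How far can the item go without triggering contact?**

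Assumption: the standard PHQ-9, nine items scored 0 to 3, one on suicidal or self-harm thoughts. The protocol names the instrument but does not print it. The other eight items can add at most 8 × 3 = 24 points.

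Points needed from the other eight items = lowest triggering total − answer on the suicidal-thoughts item. The lowest triggering total is 15 in the participant information and 16 in step 4.

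| Answer on the item | Participant information: untriggered totals | Other eight must reach | Step 4: untriggered totals | Other eight must reach |
|---|---|---|---|---|
| 1 | 1 to 14 | 15 − 1 = 14 | 1 to 15 | 16 − 1 = 15 |
| 2 | 2 to 14 | 15 − 2 = 13 | 2 to 15 | 16 − 2 = 14 |
| 3 | 3 to 14 | 15 − 3 = 12 | 3 to 15 | 16 − 3 = 13 |

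The GAD total must also stay below its cut-off: at most 9 in the participant information, at most 10 in step 4. Even with the maximum answer, the other eight items must supply 12 or 13 of 24 points before the PHQ-9 rule applies. The gap exists under both sets of cut-offs, so reconciling them would not close it.

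**3. Which surveys are exposed?**

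- *Baseline:* four sessions follow, so the XAIA alert could still catch the disclosure if the participant raises it. This is the lesser concern.
- *Week 4:* section 5.3 gives the form at the end of the sessions. The schedule in 5.1 puts it in the same column as session 4, and no session is scheduled later.
- *Month 3:* no session is scheduled with it or after it. Taking three months from study initiation as 12 to 13 weeks and subtracting the four session weeks, the form comes 8 to 9 weeks after the sessions end. The total-score rule is then the only stated trigger for contact by the study.

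With at most 20 participants there are at most 20 × 3 = 60 PHQ-9 forms, of which 20 × 2 = 40 (week 4 and month 3) have no scheduled session after them. This counts forms collected without a later session. It is not an estimate of positive answers, for which the protocol gives no rate.

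**The case against.** **The item content is not in the protocol.** True. It is an assumption about a named, standardized instrument, and the point falls if the study uses a version without that item. Nothing in the protocol suggests that it does.

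**The forms are unseen.** Appendices B to D and the participant information file could hold an item-level alert. This stands as a limit: the finding concerns the work-flow as written, not everything the study may do. If an alert exists, step 4 should still refer to it.

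**Step 3 already has a professional reading the responses, and step 4 is not worded as exclusive.** This is the strongest point. The social worker sees individual answers, holds the code list and may contact anyone. What remains is that contact after a positive answer is discretionary, whereas the same statement in a session leads to contact under step 5.

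**Other help is available.** The questionnaire carries hotline details and the follow-up forms list resources. Licensed mental health workers are available at all times. These reduce the risk but depend on the participant acting.

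**Week 4 is partly covered.** The form shares a visit with session 4, where the XAIA alert is active. This is fair, and it is why month 3 is the clearest case. An answer given on the form after that session still has no required response.

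**Coverage has a cost.** Sessions are confined to 0700 to 2000 so that staff can be reached, and no hours are set for the surveys. This stands in part: the new duty needs a response time that staffing can meet. Step 4 already creates a duty to contact after a survey, with no hours stated, so the kind of duty is not new.

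**Conclusion.** The concern holds. As written, the work-flow requires no contact by the study after a positive PHQ-9 suicidal-thoughts answer when both totals are below their cut-offs. With the maximum answer, that covers PHQ-9 totals of 3 to 15 with GAD at most 10 (step 4), or 3 to 14 with GAD-7 at most 9 (participant information). The gap is clearest at month 3, is present at week 4 and matters less at baseline.

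The conclusion rests on standard PHQ-9 content and scoring, and on there being no alert in the appendices that were not available. No frequency is claimed. Confidence is medium for those reasons. The change should be made: the safeguard is cheap, and the protocol already accepts its logic for sessions.

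**What to change.** Add to step 4 of section 5.2: any positive answer on the PHQ-9 suicidal-thoughts item, at baseline, week 4 or month 3, leads to prompt contact by the social worker whatever the PHQ-9 or GAD total, within a response time set by the clinical team. List the same trigger in the information given to participants about de-coding. If Appendices B to D already contain such an alert, refer to it in step 4 instead.

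The cost is one sentence in each place. The social worker already reviews every survey and holds the code list for at most 20 participants, so no added post should be needed, provided the response time fits the existing cover. Two downsides should be accepted openly. There may be a few more de-codings and contacts (number not known), and participants who know of the trigger may answer that item less candidly.

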## **5.3 Description of Study Procedures**

The study involves the completion of questionnaires to be done at the start and at the end of the study period and the completion of four sessions over the course of four consecutive weeks.

The overall study will last four weeks but we may contact participants up to 3 months after for follow up.

#### **Questionnaires/surveys:**

This study involves the administration of questionnaires to evaluate scoring changes for depression and anxiety symptoms as a measurement for mental health wellness before and after the intervention. This information is routinely collected as part of clinical care with the PHQ-9 and GAD-7 questionnaires. The questionnaires will be administered at baseline and at the end of the 4-week study period. As part of the initial questionnaire, there will be a set of questions that aim to determine demographics as well as work-related and home-related factors that contribute to mental health will be administered prior to the AI powered sessions. At the completion of the 4-week session a questionnaire with a set of questions evaluating the use and acceptability of the AI mental health support will be administered. Finally, participants will be sent a questionnaire including the PHQ-9 and GAD-7 along with a set of questions evaluating their interest in participating in additional sessions at 3 months. The follow-up questionnaires will also provide information on active resources for mental health available to trainees at Cedas Sinai. In total, the questionnaires should take no longer than 20 minutes to complete at the beginning and end of the study period and no longer than 10 minutes at followup. The questionnaire will be administered electronically via REDCap. The study will not collect personal identifying information. The questionnaire will also contain a link with information on how to obtain immediate mental health assistance including a hot line as provided by GME to all trainees at Cedars Sinai. This includes access to a mental health professional who is on call for any psychiatric emergencies.

We will be conducting following questionnaires.

- Patient Health Questionnaire -9 (PHQ-9) Will be administered at the beginning and end of the study as part of Appendix B, C and D.
  - o This questionnaire is validated.
  - o The questionnaire is available in languages other than English.
- General Anxiety Disorder- 7 (GASD-7) will be administered at the beginning and end of the study as part of Appendix B, C and D.
  - o This questionnaire is validated.
  - o The questionnaire is available in languages other than English.
- Work and Home Environment will be administered only at the beginning of the study as part of Appendix B.
  - o This questionnaire is not validated.
  - o The questionnaire is not available in languages other than English.
- Artificial Intelligence Session Assessment will be administered only at the end of the sessions as part of Appendix C.
  - o This questionnaire is not validated.
  - o The questionnaire is not available in languages other than English
- Post Artificial Intelligence Session Follow-up will be administered at 3 months after study initiation as part of Appendix D.
  - o This questionnaire is not validated
  - o The questionnaire is not available in languages other than English

#### **Behavioral Intervention:**

This study involves a behavioral intervention. The behavioral intervention is the completion of a self-guided AI mental health support sessions by each participant. Participants will be asked to complete the session once per week for four consecutive weeks. Each session should take 20 minutes for completion. This intervention will take place at the participant's home or at Cedars in a location with access to a web browser via computer, tablet or cellphone. Those who choose to complete the session at Cedars-Sinai, may choose to use a call room dedicated for trainees. The intervention will be implemented by participants themselves.

The behavioral intervention will be implemented in the following manner:

- Participants will use the link provided by our social worker to gain access to XAIA. They
  will then follow the 2 minute tutorial provided directly by the link to use the software on
  a web browser. Participants can use a computer, laptop, tablet or cellphone with a web
  browser to access the XAIA software.
- Participants will be asked to spend 20 minutes during each session. They may choose to spend longer than 20 minutes but no more than 60 minutes.
- Participants will be asked to complete 1 session per week during the 4-week study phase.
- Participants will be asked to complete the sessions between the hours of 0700 and 2000 in order to have immediate access to our social worker and psychiatrist if needed.
- The email with link provided to access the XAIA software will include information for access to immediate mental health assistance such as a hotline provided by GME to all trainees at Cedars Sinai (Appendix E). This includes access to a mental health professional who is on call for any psychiatric emergencies.

## 6.0 Data Collection and Management

#### 6.1 Data Procurement

Identification/Access/Abstraction

citation / 100055/1165ti uotion
☐ Members of the study team will require access to the clinical data source (e.g., electronic medical record) to identify eligible data/specimens and to conduct data abstraction or gain access to specimens.¹
□ Electronic Information Systems (EIS) Department will identify and/or abstract applicable data or specimens (e.g., RISCC website, request query of Deep6 through EIS).

 
□ Separate registry or repository will identify, abstract, and/or provide specimens and/or data to the study team.
 
☑ Other:
 

Members of the study team will only require access to data provided by the questionnaires ompleted by participants. No personal or identifying information will be used in this study.

<sup>1 Clinical records can only be accessed by study team members who are listed on the CS-IRB application and are IRB Certified.

### • Source(s) of Data/Specimens:

No medical record data will be accessed as part of this research. All data collected is from the survey/questionnaire.

### 6.2 Time Period of Data under Review

- One year
- Information will be kept for 2 years.

#### 6.3 Data Elements

- The following data points will be collected:
  - Age
  - Sex / Gender Identity
  - Race/ Ethnicity

The information to be accessed and reviewed is that which is minimally necessary to achieve the goals of this research.

HIPAA Identifiers
$\square$ No HIPAA Identifiers will be collected for this study (or select the
identifiers from the following list). The investigators will not attempt
to re-identify subjects from the collected data.
□ Medical Record Number
□ Name
☐ Address (all geographic sub-divisions smaller than state, including street
address, city county, and zip code)
☐ All elements (except years) of dates (including birthdate, admission date,
discharge date, date of death, and exact age if over 89)
⊠ Telephone Numbers
□ Fax Numbers
⊠ Email Address
□ Social Security Number
☐ Health plan beneficiary number
□ Account Number
□ Certificate or license number
☐ Vehicle identifiers and serial numbers, including license plate numbers
☐ Device identifiers and serial numbers
□ Web URL
□ Internet Protocol (IP) Address
☐ Finger or Voice Print
☐ Photographic Image (photographic images are not limited to the face)
☐ Any other characteristic that could uniquely identify the individual

